4.5.15 Optional Samples for Research Biosample Repository

4.5.15.1 Overview of the Research Biosample Repository

The Research Biosample Repository (RBR) is a centrally administered group of facilities used for the long-term storage of human biologic specimens, including body fluids, solid tissues, and derivatives thereof (e.g., DNA, RNA, proteins, peptides). The collection, storage, and analysis of RBR specimens will facilitate the rational design of new pharmaceutical agents and the development of diagnostic tests, which may allow for individualized drug therapy for patients in the future.

Specimens for the RBR will be collected from patients who give specific consent to participate in this optional research. RBR specimens will be used to achieve the following objectives:

- To study the association of biomarkers with efficacy, adverse events, or disease progression
- To increase knowledge and understanding of disease biology
- To study drug response, including drug effects and the processes of drug absorption and disposition
- To develop biomarker or diagnostic assays and establish the performance characteristics of these assays

4.5.15.2 Approval by the Institutional Review Board or Ethics Committee

Collection and submission of biological samples to the RBR is contingent upon the review and approval of the exploratory research and the RBR portion of the Informed Consent Form by each site's IRB/EC and, if applicable, an appropriate regulatory body. If a site has not been granted approval for RBR sampling, this section of the protocol (Section 4.5.15) will not be applicable at that site.

4.5.15.3 Sample Collection

The following samples will be stored in the RBR and used for research purposes, including, but not limited to, research on biomarkers related to asthma or MSTT1041A:

- Blood samples collected at the randomization visit
- Leftover blood, serum, plasma, RNA, DNA, and urine samples

The above samples may be sent to one or more laboratories for DNA extraction to enable analysis of germline mutations, somatic mutations via whole genome sequencing (WGS), next-generation sequencing (NGS), or other genomic analysis methods.

Genomics is increasingly informing researcher's understanding of disease pathobiology. WGS provides a comprehensive characterization of the genome and, along with clinical data collected in this study, may increase the opportunity for developing new therapeutic approaches. Data will be analyzed in the context of this study but will also be explored in aggregate with data from other studies. The availability of a larger dataset will assist in identification of important pathways, guiding the development of new targeted agents.

For sampling procedures, storage conditions, and shipment instructions, see the laboratory manual.

RBR specimens are to be stored until they are no longer needed or until they are exhausted. However, the RBR storage period will be in accordance with the IRB/EC-approved Informed Consent Form and applicable laws (e.g., health authority requirements).

4.5.15.4 Confidentiality

Specimens and associated data will be labeled with a unique patient identification number.

Patient medical information associated with RBR specimens is confidential and may be disclosed to third parties only as permitted by the Informed Consent Form (or separate authorization for use and disclosure of personal health information) signed by the patient, unless permitted or required by law.

Given the complexity and exploratory nature of the analyses, data derived from RBR specimens will generally not be provided to study investigators or patients unless required by law. The aggregate results of any conducted research will be available in accordance with the effective Sponsor policy on study data publication.

Data generated from RBR specimens must be available for inspection upon request by representatives of national and local health authorities and Sponsor monitors, representatives, and collaborators, as appropriate.

Any inventions and resulting patents, improvements, and/or know-how originating from the use of the RBR data will become and remain the exclusive and unburdened property of the Sponsor, except where agreed otherwise.

4.5.15.5 Consent to Participate in the Research Biosample Repository

The Informed Consent Form will contain a separate section that addresses participation in the RBR. The investigator or authorized designee will explain to each patient the objectives, methods, and potential hazards of participation in the RBR. Patients will be told that they are free to refuse to participate and may withdraw their specimens at any time and for any reason during the storage period. A separate, specific signature will be required to document a patient's agreement to provide optional RBR specimens. Patients who decline to participate will not provide a separate signature.

The investigator should document whether or not the patient has given consent to participate and (if applicable) the date(s) of consent, by completing the RBR Research Sample Informed Consent eCRF.

In the event of an RBR participant's death or loss of competence, the participant's specimens and data will continue to be used as part of the RBR research.

4.5.15.6 Withdrawal from the Research Biosample Repository

Patients who give consent to provide RBR specimens have the right to withdraw their specimens from the RBR at any time for any reason. If a patient wishes to withdraw consent to the testing of his or her specimens, the investigator must inform the Medical Monitor in writing of the patient's wishes through use of the appropriate RBR Subject Withdrawal Form and, if the trial is ongoing, must enter the date of withdrawal on the RBR Research Sample Withdrawal of Informed Consent eCRF. The patient will be provided with instructions on how to withdraw consent after the trial is closed.

[contact]

A patient's withdrawal from Study GB39242 does not, by itself, constitute withdrawal of specimens from the RBR. Likewise, a patient's withdrawal from the RBR does not constitute withdrawal from Study GB39242.

4.5.15.7 Monitoring and Oversight

RBR specimens will be tracked in a manner consistent with Good Clinical Practice by a quality-controlled, auditable, and appropriately validated laboratory information management system, to ensure compliance with data confidentiality as well as adherence to authorized use of specimens as specified in this protocol and in the Informed Consent Form. Sponsor monitors and auditors will have direct access to appropriate parts of records relating to patient participation in the RBR for the purposes of verifying the data provided to the Sponsor. The site will permit monitoring, audits, IRB/EC review, and health authority inspections by providing direct access to source data and documents related to the RBR samples.

4.6 PATIENT, TREATMENT, STUDY, AND SITE DISCONTINUATION

4.6.1 Patient Discontinuation

Patients have the right to voluntarily withdraw from the study at any time for any reason. In addition, the investigator has the right to withdraw a patient from the study at any time. For patients randomized to the double-blind treatment period, reasons for withdrawal from the study should only include the following:

- Patient withdrawal of consent at any time
- Any patient that the investigator or Sponsor considers lost-to follow up

Every effort should be made to obtain information on patients who withdraw from the study. The primary reason for withdrawal from the study should be documented on the appropriate eCRF. If a patient requests to be withdrawn from the study, this request must be documented in the source documents and signed by the investigator. Patients who withdraw from the study will not be replaced.

Patients who discontinue the study prematurely should return to the clinic for an early termination visit 4 weeks after the last dose of study drug and should be asked to return for safety follow-up visits (see [Appendix 1](#)).

Patients who receive placebo during the run-in period but fail to meet the additional eligibility criteria for the double-blind treatment period (see Section [4.1.1.2](#) and Section [4.1.2.2](#)) should be discontinued from the study and prohibited from re-screening. In addition, these patients should be informed that the first dose given at Visit 2 was a placebo and, therefore, they are not required to return for follow-up visits.

4.6.2 Study Treatment Discontinuation

Reasons for discontinuation of study drug may include, but are not limited to, the following:

- Any medical condition that the investigator or Sponsor determines may jeopardize the patient's safety if he or she continues to receive study drug (see Section [5.1.2](#) for further guidance)
- Investigator or Sponsor determines it is in the best interest of the patient

- Cases of potential drug-induced liver injury that include an elevated ALT or AST in combination with either an elevated bilirubin or clinical jaundice, as defined by Hy's Law (see Section 5.3.5.7)
- Pregnancy

The primary reason for study treatment discontinuation should be documented on the appropriate eCRF. Patients who discontinue study treatment prematurely will not be replaced.

Every attempt should be made to prevent non-compliance with the study protocol. Before permanently discontinuing study treatment, either initiated by the patient or the investigator, an interruption should be considered. Patients who have temporarily discontinued study drug medication for any reason should restart as soon as medically justified in the opinion of the investigator (see Section 5.1.2).

Patients who discontinue study treatment prematurely should be asked to continue with all scheduled study assessments through the end of the study. Patients who are unable or unwilling to complete the study assessments in the double-blind treatment period should complete an early termination visit and both safety follow-up visits (see Appendix 1).

4.6.3 Study and Site Discontinuation

The Sponsor may stop the study for medical or ethical reasons. Possible reasons for terminating the study may include, but are not limited to, the following:

- The incidence or severity of adverse events in this or other studies indicates a potential health hazard to patients
- Patient enrollment is unsatisfactory

The Sponsor will notify the investigator if the Sponsor decides to discontinue the study.

The Sponsor has the right to close a site at any time. Reasons for closing a site may include, but are not limited to, the following:

- Excessively slow recruitment
- Poor protocol adherence
- Inaccurate or incomplete data recording
- Non-compliance with the International Conference on Harmonisation (ICH) guideline for Good Clinical Practice
- No study activity (i.e., all patients have completed the study and all obligations have been fulfilled)

5. ASSESSMENT OF SAFETY

5.1 SAFETY PLAN

MSTT1041A is not approved anywhere in the world, and clinical development is ongoing. The safety plan for patients in this Phase IIb study is based on clinical experience with MSTT1041A in completed Phase I studies. As reported in the MSTT1041A Investigator's Brochure, there are no identified risks associated with MSTT1041A and there were no serious adverse events or adverse events that led to treatment discontinuation in healthy subjects who received single (n=79) or multiple (n=31) SC doses of MSTT1041A ranging from 2.1 mg to 560 mg and IV doses ranging from 210 to 700 mg, or atopic asthma patients (n=2) who received a single 700 mg IV dose of MSTT1041A. Potential risks for MSTT1041A are described below. Please refer to the MSTT1041A Investigator's Brochure for a complete summary of safety information.

Measures will be taken to ensure the safety of patients participating in this study, including stringent eligibility criteria that are designed to exclude patients at higher risk for toxicities (see Section 4.1) and close monitoring of patients, including assessment of the nature, frequency, and severity of adverse events. In addition, an iDMC will monitor safety data on an ongoing basis (see Section 3.1.2 for details). Guidelines for managing adverse events, including criteria for treatment interruption or discontinuation, are provided below.

5.1.1 Potential Risks for MSTT1041A

5.1.1.1 Immunogenicity

As with administration of any exogenous protein, there is potential risk for development of anti-drug antibodies (ADAs). Such antibodies can be neutralizing with potential for reduced therapeutic effect of the drug or the endogenous protein and/or sensitizing with potential for adverse events.

Serum samples will be collected at protocol-defined intervals to monitor for the development of ADAs. Patients who test positive for antibodies and have clinical sequelae that are considered potentially related to an ADA response may also be asked to return for additional follow-up testing.

5.1.1.2 Hypersensitivity Reactions and Anaphylaxis/Hypersensitivity-Like Reactions

Hypersensitivity reactions and anaphylaxis have been described with SC administration of monoclonal antibodies (Corominas et al. 2014). Signs and symptoms may include acute onset (minutes to several hours) of one or more of the following: respiratory compromise, reduced blood pressure, skin-mucosal involvement, or gastrointestinal symptoms (Sampson et al. 2006).

The potential for hypersensitivity to MSTT1041A in humans is unknown.

No allergic reactions associated with MSTT1041A were observed following a single IV dose or repeat SC doses in cynomolgus monkeys and healthy volunteers. However, as with any large-molecule therapeutic, administration of MSTT1041A may result in systemic reactions. Systemic reactions to large-molecule therapeutics can be IgE or non-IgE mediated or due to the release of cytokines and are generally characterized by signs and symptoms such as skin rash, urticaria, pruritus, local or diffuse erythema, angioedema, fever, chills, cough, dyspnea, wheezing, bronchospasm, nausea, vomiting, diaphoresis, chest pain, tachycardia or bradycardia, and/or hypotension, which can be severe or life threatening. Effects typically occur during or within several hours after drug administration, but they may be delayed.

Patients with a history of anaphylaxis, hypersensitivities, or drug allergies will be excluded from the study according to the exclusion criteria listed in Section 4.1.2.1.

Investigators and health care professionals administering MSTT1041A should recognize and manage the signs and symptoms of such reactions and should be familiar with Sampson's criteria for defining anaphylaxis (Sampson et al. 2006). All potential cases of anaphylaxis should be captured on the Adverse Event eCRF as instructed in Section 5.2 and Section 5.3. Investigators and health care professionals should accurately report these events immediately to the Sponsor as SAEs if appropriate. Health care professionals should also instruct patients on how to recognize the symptoms of any such events and to contact a health care provider or seek emergency care in case of any such symptoms.

5.1.1.3 Injection-Site Reactions

Injection-site reactions have been described with SC administration of monoclonal antibodies (Corominas et al. 2014). Signs and symptoms may include pain, itching, erythema, and swelling at the injection site. The reaction may be immediate, although it usually appears within 24–48 hours with variable incidence according to the drug administered.

No clinically significant injection-site reactions associated with MSTT1041A were observed following single or repeat doses in cynomolgus monkeys or healthy volunteers. However, as with any large-molecule therapeutic, administration of MSTT1041A may result in local reactions. Local reactions may include signs and symptoms such as redness, tenderness or pain, bruising, warmth, swelling, pruritus, or infection.

5.1.1.4 Infection

The intended mechanism of action of MSTT1041A suggests inhibitory effects on immune responses mediated by Th2 cells, leading to the possibility of a decrease in the protective response to infection. MSTT1041A may have additional, unanticipated immune-mediated side effects.

5.1.1.5 Metabolic or Cardiovascular Effects

Published studies involving mouse models of cardiovascular disease or in vitro culture systems describe potential cardioprotective and atheroprotective roles of the IL-33/ST2 axis (Sanada et al. 2007; Miller et al. 2008; Seki et al. 2009; McLaren et al. 2010; Wasserman et al. 2012). However, studies with conflicting data exist (Abston et al. 2012; Demyanets et al. 2013; Martin et al. 2015). In nonclinical toxicology and safety pharmacology studies with cynomolgus monkeys, no biologically significant changes were exhibited by MSTT1041A.

There is evidence supporting use of the soluble form of the ST2 receptor (sST2) as a prognostic biomarker of cardiovascular disease outcome (Sabatine et al. 2008; Shah and Januzzi 2010; Weir et al. 2010). Although published findings suggest a possible risk of exacerbation of existing cardiovascular disease in humans, there are no identified cardiovascular risks associated with inhibiting the IL-33/ST2 axis in humans.

Patients with certain forms of cardiovascular disease will be excluded from the study. To observe for any immediate cardiovascular toxicity, ECGs will be monitored (in triplicate). In addition, fasting glucose, HbA_{1c}, and lipid panels will be monitored to observe and/or identify any effects of MSTT1041A on cardiovascular risk factors.

During the study, investigators and healthcare professionals administering MSTT1041A should accurately report all Major Adverse Cardiac Events (MACE) on the Adverse Event eCRF, as instructed in Section 5.2 and Section 5.3, and should report these events immediately to the Sponsor as SAEs if appropriate. Major Adverse Cardiac Events include death due to cardiovascular causes, non-fatal myocardial infarction, non-fatal stroke or transient ischemic attack (TIA), unstable angina or chest pain requiring hospitalization, coronary revascularization, and congestive heart failure (CHF) requiring hospitalization.

5.1.2 Management of Patients Who Experience Specific Adverse Events

5.1.2.1 Treatment Interruption

Study treatment may be temporarily suspended in patients who experience toxicity considered to be related to study drug. If study treatment has been withheld for two or more consecutive dosing visits because of toxicity, the patient should be discontinued from study treatment. However, if the adverse event(s) that led to withholding dosing shows clear evidence of improvement, treatment may be resumed following discussion with and approval by the Medical Monitor. Study treatment may be suspended for reasons other than toxicity (e.g., surgical procedures), but must be approved by the Medical Monitor. The investigator and the Medical Monitor will determine an acceptable length of time for the treatment interruption.

5.1.2.2 Guidelines for Treatment Interruption or Discontinuation for Patients Who Experience Hepatotoxicity

Table 4 provides specific guidelines for withholding or discontinuing study drug for patients who experience hepatotoxicity.

Table 4 Guidelines for Treatment Interruption or Discontinuation for Patients Who Experience Hepatotoxicity

Event	Action to Be Taken
Hepatotoxicity	
ALT or AST increase that meets Hy's Law criteria: ALT or AST >3 × ULN in combination with TBILI >2 × ULN or clinical jaundice	Discontinue MSTT1041A.
If criteria for Hy's law are not met: ALT or AST increase that meets at least one of the following criteria: 
 • >8 × ULN • >5 × ULN for ≥2 weeks • >3 × ULN with clinical signs or symptoms that are consistent with hepatitis (e.g., right upper quadrant pain or tenderness, fever, nausea, vomiting, jaundice) 	Withhold MSTT1041A. Treatment may be resumed if an alternative cause is identified and laboratory values have resolved to those at the randomization visit. If signs or symptoms recur, permanently discontinue MSTT1041A.
If criteria for Hy's law are not met: TBILI >3 × ULN	Withhold MSTT1041A. Treatment may be resumed if an alternative cause is identified and laboratory values have resolved to those at the randomization visit. If signs or symptoms recur, permanently discontinue MSTT1041A.
Alkaline phosphatase >3 × ULN	Withhold MSTT1041A. Treatment may be resumed if an alternative cause is identified and laboratory values have resolved to those at the randomization visit. If signs or symptoms recur, permanently discontinue MSTT1041A.

TBILI=total bilirubin; ULN=upper limit of normal.

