5.3.5.7 Abnormal Liver Function Tests

The finding of an elevated ALT or AST ($>3 \times \text{ULN}$) in combination with either an elevated total bilirubin ($>2 \times \text{ULN}$) or clinical jaundice in the absence of cholestasis or other causes of hyperbilirubinemia is considered to be an indicator of severe liver injury (as defined by Hy's law). Therefore, investigators must report as an adverse event the occurrence of either of the following:

- Treatment-emergent ALT or AST $>3 \times \text{ULN}$ in combination with total bilirubin $>2 \times \text{ULN}$
- Treatment-emergent ALT or AST $>3 \times \text{ULN}$ in combination with clinical jaundice

The most appropriate diagnosis or (if a diagnosis cannot be established) the abnormal laboratory values should be recorded on the Adverse Event eCRF (see Section 5.3.5.2) and reported to the Sponsor immediately (i.e., no more than 24 hours after learning of the event), either as a serious adverse event or an adverse event of special interest (see Section 5.4.2).

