4.7.2 Adverse Events

Verbatim descriptions of treatment-emergent adverse events will be coded using the latest version of MedDRA. A treatment-emergent adverse event is defined as any new adverse event or any worsening of an existing condition with an onset date on or after the first study drug administration date. Summaries of treatment-emergent events will be provided for each of the following categories:

- All adverse events
- All adverse events by most extreme severity
- Adverse events assessed as related to study treatment by the investigator
- All serious adverse events
- All suspected unexpected serious adverse events
- Adverse events that are a result of an error in study drug administration
- Adverse events leading to discontinuation of study treatment
- Adverse events leading to study discontinuation
- Adverse events of special interest

The adverse events of special interest will be identified as follows. Summaries will include tabulations by Medical Dictionary for Regulatory Activities (MedDRA) terms and listings, as appropriate.

- Cases of potential drug-induced liver injury that include an elevated alanine aminotransferase (ALT) or aspartate aminotransferase (AST) in combination with either an elevated bilirubin or clinical jaundice, as defined by Hy's law.
- Suspected transmission of an infectious agent by the study drug, as defined below
Any organism, virus, or infectious particle (e.g., prion protein transmitting transmissible spongiform encephalopathy), pathogenic or non-pathogenic, is considered an infectious agent. A transmission of an infectious agent may be suspected from clinical symptoms or laboratory findings that indicate an infection in

a patient exposed to a medicinal product. This term applies only when a contamination of the study drug is suspected.

- Potential major adverse cardiac events (MACE) will be identified as follows.

Death due to cardiovascular causes, non-fatal myocardial infarction, non-fatal stroke or transient ischemic attack (TIA), unstable angina or chest pain requiring hospitalization, coronary revascularization, and congestive heart failure (CHF) requiring hospitalization.

In addition, patient deaths and the primary cause of death will be listed, as well as any cases of pregnancy, anaphylaxis, anaphylactoid, and hypersensitivity.

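### Hy's law is defined inconsistently in the protocol sections on stopping study drug, and Table 4 overlaps with itself, so some patients meet different instructions

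*Protocol*

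**What the plan says.** **Table 4, row 1 (Protocol Section 5.1.2.2).** The trigger is "ALT or AST >3 × ULN in combination with TBILI >2 × ULN or clinical jaundice" and the action is "Discontinue MSTT1041A". The row has no exception and no resumption clause.

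**Table 4, rows 2 and 3 (ALT/AST and bilirubin).** Both apply only when Hy's law is not met. Row 2 needs ALT or AST >8×ULN, or >5×ULN for at least 2 weeks, or >3×ULN with hepatitis-type symptoms, for which the examples are "e.g., right upper quadrant pain or tenderness, fever, nausea, vomiting, jaundice". Row 3 needs bilirubin >3×ULN. The action is to withhold, and "Treatment may be resumed if an alternative cause is identified and laboratory values have resolved to those at the randomization visit".

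**Table 4, row 4.** The trigger is "Alkaline phosphatase >3 × ULN". The action is the same as in rows 2 and 3, but the row carries no Hy's law qualifier.

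**Section 5.3.5.7.** The opening sentence uses the same thresholds but adds a condition: the bilirubin finding "or clinical jaundice in the absence of cholestasis or other causes of hyperbilirubinemia is considered to be an indicator of severe liver injury". The two reporting bullets that follow repeat the thresholds without that condition.

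**Section 4.6.2.** Among the reasons for stopping study drug are raised transaminases "in combination with either an elevated bilirubin or clinical jaundice, as defined by Hy's Law (see Section 5.3.5.7". Section 5.2.3 defines the corresponding adverse event of special interest (AESI) through the same cross-reference.

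**SAP Section 4.7.2.** The same event is summarised "in combination with either an elevated bilirubin or clinical jaundice, as defined by Hy's law", with no section cited.

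**The concern.** The same term carries two meanings, and within Table 4 it separates discontinuing from withholding. Row 1 states the bare pattern. The section that 4.6.2 points to for the meaning of Hy's law leaves out patients whose raised bilirubin has another explanation. An identified alternative cause is also one of the conditions for resuming under the withhold rows. The patients on whom the two definitions disagree are therefore those for whom resumption could come into question.

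What is at stake is whether a patient with a liver signal is taken off study drug, withheld and possibly re-exposed, or covered by no row, depending on which section the investigator opens.

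**Working it through.** No figure is involved, so the check sets the passages side by side and applies Table 4 under each definition. The thresholds come from Table 4 and Section 5.3.5.7. The patient values are illustrative assumptions, in multiples of ULN. Each patient is assumed to have a documented cholestatic or other cause for the raised bilirubin.

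| Case | Assumed values | Hy's law as in Table 4 row 1 | Hy's law as in the opening sentence of 5.3.5.7 |
|---|---|---|---|
| A | ALT 4, bilirubin 3.5, alkaline phosphatase 2, no symptoms | 4 > 3 and 3.5 > 2: discontinue | Not met. Bilirubin row: 3.5 > 3, so withhold, may resume |
| B | ALT 4, bilirubin 2.5, alkaline phosphatase 2, no symptoms | 4 > 3 and 2.5 > 2: discontinue | Not met. ALT is not above 5 or 8, there are no symptoms, 2.5 is not above 3, and 2 is not above 3: no row applies |
| C | ALT 4, bilirubin 2.5, alkaline phosphatase 4 | Row 1: discontinue. Row 4 also applies (4 > 3): withhold, may resume | Not met. Row 4: withhold, may resume |
| D | ALT 4, clinical jaundice | Row 1: discontinue. The jaundice example in row 2 cannot be reached | Not met. Row 2: withhold, may resume |

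Three things follow.

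1. **The definition changes the instruction.** Case A moves from discontinue to withhold with possible resumption. Case B moves from discontinue to no Table 4 row.

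2. **Table 4 does not settle the matter by itself.** Row 2 applies only when Hy's law is not met, yet it lists jaundice with ALT or AST >3×ULN. On row 1's wording that combination always meets Hy's law. The example has a use only if some exclusion such as the one in 5.3.5.7 is read into the table, which gives an investigator a textual reason to do so.

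3. **The alkaline phosphatase row can apply together with row 1.** In case C one patient meets a discontinue row and a withhold-and-may-resume row on Table 4's own wording. No order of precedence is given.

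For comparison, the QT rule in Section 5.1.2.3 writes out an exception for a clear alternative cause. Table 4 row 1 has none, and the reader cannot tell whether the silence is deliberate.

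**The case against.** The strongest reply is that there is one operative rule. Section 4.3.2.1 names Section 5.1.2.2 as the specific guidance for hepatotoxicity. Row 1 spells out its own criteria, so the natural reading of the later rows is that they refer back to it. Section 4.6.2 is a permissive, non-exhaustive list, and its first item points to Section 5.1.2, which contains Table 4. A patient discontinued under row 1 breaches neither section. Section 5.3.5.7 is a reporting section. All of this stands, and it rules out describing the protocol as having two complete stopping rules. It does not explain the unreachable jaundice example or the unqualified alkaline phosphatase row, both of which are inside Table 4.

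Four stronger readings are tempting, and the documents do not support them:

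- **Stopped for good against only withheld.** Row 1 does not say permanently; that word appears only in the withhold rows. Section 4.3.2.1 allows patients who stop for intolerance to resume if the event is judged unrelated and the investigator and Medical Monitor agree. Permanent stopping under row 1 is an inference.
- **Opposite actions in every case with another cause.** Case B shows that a patient excluded from Hy's law may meet no withhold row.
- **A changed AESI count by dose.** The reporting bullets in 5.3.5.7 use the bare pattern, so capture does not depend on the exclusion. What is left is that SAP 4.7.2 does not say which definition classifies a case.
- **Jaundice as a conflict of action within Table 4.** On row 1's wording the row 2 example is redundant and changes no action. It matters as a sign that the table may be read with an exclusion.

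**Conclusion.** The point holds as an inconsistency of definition with practical consequences for some patients. Table 4 is the operative guidance. The sections that define Hy's law elsewhere send the reader to a narrower definition, and Table 4's rows overlap. For a patient with another identified cause, the instruction can change from discontinue to withhold with possible resumption, or from discontinue to no row. A patient with alkaline phosphatase >3×ULN can meet two different actions at once.

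The number of patients affected cannot be estimated, because the documents give no frequency; that it will be small is an assumption. The case values are also assumed. The comparison takes the exclusion in 5.3.5.7 to cover both the bilirubin limb and the jaundice limb. The sentence could be read as attaching it to jaundice alone, in which case A and B would not diverge but D still would. Correction is worthwhile because each case concerns possible re-exposure after a liver signal and the remedy is wording. Which clinical rule should apply is not judged here.

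**What to change.** Reconcile Table 4, Section 4.6.2, Section 5.2.3 and Section 5.3.5.7 to a single definition of Hy's law, and have each place cite it. In particular:

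- State in Table 4 row 1 whether the exclusion of cholestasis and other causes applies.
- Make the jaundice example in row 2 consistent with that answer.
- State how the alkaline phosphatase row relates to row 1, and give an order of precedence when more than one row is met.
- Make the opening sentence and the reporting bullets of 5.3.5.7 agree, or say that reporting is deliberately on the bare pattern.
- In SAP Section 4.7.2, cite the reconciled definition.

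The clinical content is the sponsor's decision. The cost is a protocol wording change and one cross-reference in the SAP. No new data are needed.
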